### **2.1.2 Inclusion Criteria for Genetics Research**

For inclusion in the optional genetics research study patients must fulfil the following criteria:

11. Provision of optional genetics research informed consent

If a patient declines to participate in any optional component of the study, there will be no penalty or loss of benefit to the patient, and they will not be excluded from any other aspect of the main study

### **2.1.3 Module 3-Specific Inclusion Criteria**

For inclusion in Module 3 study patients must also fulfil the following criteria:

12. Patients with Wnt ligand-dependent solid tumours, defined as:
  - Biliary tract cancers
  - Thymus cancers (thymic and thymoma WHO classification)
  - Any solid tumour with documented aberration in RNF43 and/or RSPO from central pre-screening or from a recognised panel approved by the Sponsor. See Section 5.4.2.4 and Appendix 10 for more details

Patients willing to have mandatory skin biopsies at baseline and on one occasion while on study treatment. See schedule of assessments (Appendix 9) for details.

## **2.2 Exclusion Criteria**

### **2.2.1 Core Exclusion Criteria**

For inclusion in all modules of the study, all patients must not enter the study if any of the following exclusion criteria are fulfilled:

1. Prior therapy with a compound of the same mechanism of action as RXC004

2. No other anti-cancer therapy, or other investigational product is permitted other than the agent(s) described in the relevant study module.
  - During the study period, patients using allowed hormonal therapy should maintain a constant dose and should not change existing regimen.
  - If a change in hormonal therapy is indicated, e.g. due to intolerable adverse effects, the regimen may be modified but change should be minimized thereafter.
3. Patients with persistent grade 2 or higher diarrhoea (any cause) that has not resolved or improved with appropriate treatment prior to study enrolment
4. Patients at higher risk of bone fractures, including;
  - Patients with bone metastases
  - Patients with  $\beta$ -CTX (bone turnover marker) of  $> 1000$  pg/mL
  - Patients with Vitamin D [25(OH)D3] deficiency defined as  $< 30$ nmol/L ( $< 12$ ng/mL). [Note - Patients who fail on this criteria **alone** can be retested within the screening window (see Sec 3.4.1.2)]
  - Patients with a corrected total serum calcium level of  $< 2$  mmol/L and serum magnesium level of  $< 0.60$  mmol/L
  - Patients with osteoporosis (as defined by a T-score of  $< -2.5$  at L/R total hip, L/R femoral neck, or lumbar spine (L1-4) by DEXA scan) or history of fragility fractures (any fracture occurring with low-level trauma or as a result of falling  $<$  standing height and any  $\geq$  grade 2 vertebral fracture on VFA)
  - Patients with a prior diagnosis of hyperparathyroidism, Pagets disease or Osteomalacia, considered to have no increased bone fragility risk, may be included only after consultation with the Sponsor's Medical Monitor.
  - Patients who have received treatment for type 2 Diabetes Mellitus with a Thiazolidinedione peroxisome proliferator-activated receptor gamma agonist (e.g. pioglitazone or rosiglitazone) within 4 weeks prior to study drug dosing.
  - Patients who have received oral or intravenous (i.v.) glucocorticoids for  $> 4$  weeks at daily doses equivalent to  $\geq 7.5$  mg of oral (p.o.) prednisolone within 6 weeks prior to study drug dosing
5. Patients receiving radiation to more than 30% of the bone marrow, direct radiation to their spine or pelvis, or with a wide field of radiation within 4 weeks of the first dose of study treatment.
6. Female patients who are pregnant or breast-feeding at entry
7. QTcF prolongation ( $> 470$  msec)
8. Patients with any known uncontrolled inter-current illness including ongoing or active clinically significant infections, symptomatic congestive heart failure (with an Ejection Fraction (EF)  $\leq 50\%$  or the institutional lower limit of normal whichever is lower), hypertension, unstable angina pectoris, cardiac arrhythmia, or psychiatric illness/social situations that would limit compliance with study requirements
9. Patients with any of the following medications within 4 weeks prior to enrolment:
  - Anti-neoplastic agents

- Immunotherapy (mAbs, Interferons, Cytokines [except GCSF])
  - Immunosuppressants (e.g. cyclosporin, rapamycin, tacrolimus, rituximab, alemtuzumab, natalizumab, etc.).
  - Another investigational drug
10. Patients with any known severe allergies (e.g. anaphylaxis) to any active or inactive ingredients in the study drugs

### **2.2.2 Module 2: RXC004- and Nivolumab-Specific Exclusion Criteria**

In addition to the core exclusion criteria, patients must not enter Module 2 if any of the following exclusion criteria are fulfilled:

11. Patients with any contraindication to the use of Nivolumab as per approved county label (Summary of Product Characteristics or equivalent)
12. Patients with active or prior documented autoimmune disorders, drug-induced immune disorders, or inflammatory disorders within the past 5 years, including inflammatory bowel disease, rheumatoid arthritis, immune hepatitis, pneumonitis, Grave's disease, lupus and celiac disease. The following are exceptions to this criterion;
  - (a) Patients with vitiligo or alopecia
  - (b) Patients with type I diabetes mellitus
  - (c) Patients with residual hypothyroidism due to autoimmune condition only requiring hormone replacement
  - (d) Patients with psoriasis not requiring systemic treatment, or conditions not expected to recur in the absence of an external trigger.
  - (e) Patients with celiac disease controlled by diet alone
13. Patients with active infections, including tuberculosis, hepatitis B, hepatitis C or human immunodeficiency virus
14. Use of any live vaccines against infectious diseases (eg, influenza nasal formulation, varicella) within 4 weeks (28 days) of initiation of study treatment
15. Patients with body weight <40kg
16. Patients with a history of allogeneic organ transplant or active primary immunodeficiency
17. Patients with a known hypersensitivity to Nivolumab or any of the excipients of the product

### **2.3 Subject Restrictions**

The following restrictions apply while the patient is receiving study treatment and for the specified times before and after:

- Patients must fast (water to drink only) from at least 2 hours prior to taking a dose to at least 1-hour post-dose for all doses
- Patients taking RXC004 are advised to avoid exposure to direct sunlight and the use of tanning equipment.

#### Male patients:

- Men must use a condom (with spermicide) during the study, and for 1 week after the last dose of study drug, with all sexual partners
- Where a sexual partner of a male participant is a WOCBP who is not using effective contraception, men must use a condom (with spermicide) during the study and for 6 months after the last dose of a study drug
- Must not donate sperm for 6 months after the last dose of study drug

#### Female patients

- Women with evidence of non-child-bearing potential at screening have no restrictions around contraception

Women of child-bearing potential must use enhanced contraception during the study, and for 6 months after the last dose of study drug, with all male sexual partners. Highly effective methods of contraception must be used, which include having a vasectomised partner, sexual abstinence (defined as refraining from heterosexual intercourse during the study and for 5 months after the last dose of study drug. The reliability of sexual abstinence needs to be evaluated by the Investigator, in relation to the duration of the study and the preferred/usual lifestyle of the patient) or one of the following: hormonal contraceptives which inhibit ovulation (oral, injectable, transdermal, intravaginal or implants), intrauterine device (IUD), intrauterine hormone-releasing system (IUS) (e.g., Mirena), or bilateral tubal occlusion.

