### **1.7.1.2.4 Reproductive and Teratogenic Toxicity**

No reproductive toxicology or teratogenic studies have been conducted with RXC004 to date, and it is unknown whether the drug is excreted in human milk. Therefore, WOCBP and men should agree to use adequate contraception prior to study entry and for the duration of study participation, and women who are breast feeding are excluded from the study. Both women and men should be fully informed of the lack of reproductive toxicity testing, and women must have a negative pregnancy test prior to enrolment.

Please refer to the IB for further information.

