### **4.3.4 Pregnancy**

A Pregnancy Report Form (or equivalent) must be completed for all pregnancies that occur from the time of first study drug dose until 6 months after the last dose of study drug(s) received, including any pregnancies that occur in the female partner of a male study patient. Additionally, all pregnancies should be reported that occur in a male patient's partner if the estimated date of conception occurred after the male patient's first dose of study drug. The form must be transmitted to the Drug Safety Department of IQVIA within 48 hours of becoming aware of the pregnancy. All pregnancies will be monitored for the full duration; all perinatal and neonatal outcomes should be reported. Infants should be followed for a minimum of 8 weeks after their delivery.

Collection of data on the CRF: All pregnancies (as described above) that occur within 30 days of the last dose of study drug(s) will also be recorded as an AE. Abortion (whether spontaneous, therapeutic, or planned) should be reported as an SAE. Congenital anomalies or birth defects should be reported as SAEs.

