#### **5.4.5 Intermittent Schedule Rationale**

[figure not shown]
Redx have previously demonstrated that RXC004 is efficacious when delivered on a 5 days on/2 days off schedule in multiple mouse oncology models (see Figure 6 below). Due to differences in half-life between mouse and human, with RXC004 having a significantly longer half-life in man ( 11 to 13 h compared to 2.4 to 3.4 h in mice) this pre-clinical schedule is most closely matched by the 4 days on/3 days off schedule in man.

Figure 6      Dose-dependent effects of RXC004 in B16F10/C27BL/6 syngeneic model and the SNU-1411 xenograft model.

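### Protocol Section 2.3 requires contraception for 6 months after the last dose but defines abstinence, an accepted method, as lasting only 5 months

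*Protocol*

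**What the plan says.** Protocol Section 2.3 (Subject Restrictions, Female patients) sets the general rule: "Women of child-bearing potential must use enhanced contraception during the study, and for 6 months after the last dose of study drug". The sentence that follows lists the accepted methods: "Highly effective methods of contraception must be used, which include having a vasectomised partner, sexual abstinence" and several others. Abstinence is then explained in parentheses as "defined as refraining from heterosexual intercourse during the study and for 5 months after the last dose of study drug". The same parenthesis asks the Investigator to judge how reliable abstinence is for the individual patient.

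Other provisions with a post-treatment period:

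- **Section 2.3, Male patients.** Where the partner is a woman of child-bearing potential who is not using effective contraception, condoms are required "during the study and for 6 months after the last dose of a study drug". Sperm donation is also barred for 6 months. A separate general condom rule, covering all partners, runs for 1 week after the last dose.
- **Section 4.3.4 (Pregnancy).** Pregnancies are reported from the first dose "until 6 months after the last dose of study drug(s) received".

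Section 1.7.1.2.4 gives the background: "No reproductive toxicology or teratogenic studies have been conducted with RXC004 to date".

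**The concern.** Two consecutive sentences of operative text give different end dates for what should be one obligation. Abstinence is the only listed method that carries its own duration. The others (vasectomised partner, hormonal methods, intrauterine device or system, tubal occlusion) take theirs from the general rule.

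A site that copies the abstinence definition into patient counselling, or a patient who is told only that definition, could stop at 5 months and believe she has complied. Because the drug has had no reproductive toxicity testing, contraception is a main safeguard against exposure in pregnancy, and the instruction should give a single figure.

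**Working it through.** The protocol derives neither duration, so there is no calculation to reproduce. The check is a comparison of the stated periods, followed by a rough measure of the exposure at stake.

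**Step 1. Periods after the last dose, side by side**

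| Provision | Section | Period |
|---|---|---|
| Contraception, women of child-bearing potential | 2.3, Female patients | 6 months |
| Definition of abstinence, same women | 2.3, Female patients | 5 months |
| Condom use, partner of child-bearing potential not using effective contraception | 2.3, Male patients | 6 months |
| Ban on sperm donation | 2.3, Male patients | 6 months |
| Condom use, all partners | 2.3, Male patients | 1 week |
| Pregnancy reporting | 4.3.4 | 6 months |

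**Step 2. Are the first two rows comparable?** Yes. They cover the same women and start from the same event, the last dose of study drug. The gap is 6 − 5 = 1 month.

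**Step 3. Is the shorter period explained?** Neither the protocol nor the SAP gives a reason for a shorter period under abstinence. The 1-week condom rule for men does not supply one: it is a general rule for all partners, and 6 months replaces it in the case where the partner could conceive without effective contraception.

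**Step 4. How much RXC004 exposure is at stake?** Section 5.4.5 gives the half-life in man as 11 to 13 h. Taking five half-lives as a conventional washout:

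- lower end: 5 × 11 h = 55 h; 55 / 24 = 2.3 days
- upper end: 5 × 13 h = 65 h; 65 / 24 = 2.7 days

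On this measure RXC004 is cleared long before month 5. The documents give no half-life for nivolumab, so the same step cannot be done for Module 2.

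**Step 5. Effect of the correction.** With 6 months in the definition, the gap is 6 − 6 = 0 months, and the definition agrees with the general rule beside it.

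**The case against.** The strongest reply is that the mandatory sentence governs. A reader of the whole paragraph applies 6 months, and a woman who ends abstinence at 5 months must still use another listed method in month 6. The Investigator's review of abstinence is a further check. This stands, and it is why the point is a conflict of figures and not a gap in cover.

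The exposure arithmetic also works against any claim of material harm under monotherapy. That stands too.

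Three further objections carry some weight:

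- **The supporting provisions are not uniform.** Men have a 1-week rule as well, and a pregnancy-reporting window need not equal a contraception period. The case therefore rests mainly on the two adjacent sentences; the other sections show only that 6 months is the usual figure where conception is the concern.
- **Section 1.7.1.2.4 describes contraception as covering study participation, with no period after the last dose.** That is background text and not the operative restriction, and it does not make 5 months correct.
- **The origin of either figure is not shown.** For Module 2 the protocol defers to nivolumab prescribing information, which was not available. The intended number is therefore inferred. Aligning to the mandatory sentence is the conservative choice, because it never shortens protection.

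None of these supplies a reason for the two sentences to differ.

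**Conclusion.** The inconsistency is real. Section 2.3 states 6 months and 5 months for the same women from the same starting point, a difference of 1 month for one listed method. It is a minor point: a wrong figure in an operative safety restriction, with the general rule still in force.

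The added RXC004 risk is small, given clearance within about 3 days on the stated half-life. No exposure conclusion is drawn for nivolumab. The documents do not say how many women are of child-bearing potential or rely on abstinence, so the number affected cannot be given. Endpoints, dose decisions and analyses are untouched.

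The conclusion that 5 months is the figure to change assumes that the mandatory sentence expresses the sponsor's intent.

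**What to change.** In Protocol Section 2.3 (Female patients), change 5 months to 6 months in the definition of abstinence. Check the consent form, which was not available for this review, and make the same change if it repeats the 5-month figure.

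The cost is one number in the protocol and possibly one in the consent form. The SAP needs no change.

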### **2.3.1 Concomitant Treatments**

All medications used during the study and taken within 30 days of the screening visit will be recorded on the CRF.

Information on any treatment in the 4 weeks prior to starting study treatment and all concomitant treatments given during the study, with reasons for the treatment, will be recorded in the CRF. If medically feasible, patients taking regular medication should be maintained on it throughout the study period.

Concomitant medication may be given as medically indicated within 30 days prior to administration of the study drug or within 5 half-lives of the chemical entity prior to

administration of the study drug, whichever is longer with the exception of prohibited concomitant medication (see Section Prohibited Concomitant Medication 2.3.1.1)

### **2.3.1.1 Prohibited Concomitant Medication**

The following concomitant medication is prohibited without approval from the Sponsor Physician:

- The use of any natural/herbal products or other ‘folk remedies’ should be discouraged; approval required by Sponsor Physician
- No growth factor support, blood products or prophylactic antibiotics are permitted during the DLT assessment periods in the study. Following this, it may be permitted following discussion with the PI and the Sponsor
- No other chemotherapy, hormonal therapy (HRT and stable treatment of > 6 months with GnRH analogues are acceptable), or other investigational product is permitted other than the combination agent(s) described in the relevant study module
- Live virus and bacterial vaccines should not be administered, e.g. yellow fever, measles, influenza nasal spray, rubella, mumps, typhoid, *Mycobacterium tuberculosis* (BCG), *Yersinia pestis* (EV series) whilst the patient is receiving study medication and during the 28-day follow-up period following IP discontinuation. An increased risk of infection by the administration of these vaccines has been observed with conventional chemotherapy and the effects with RXC004 are unknown. The administration of killed vaccines is allowed. Examples of killed vaccines are cholera, bubonic plague, polio, hepatitis A and rabies
- Patients must not receive any other investigational drugs while on this study, other than the combination agent(s) described in the relevant study module
- The use of some CYP3A4 inhibitors and inducers should be restricted throughout the study, as RXC004 is observed to be exclusively metabolised by CYP3A4. For a list of prohibited CYP3A4 inhibitors and inducers please refer to Appendix 7.
- For patients enrolled in Module 2, patients should not receive concurrent immunosuppressive medications. The following exceptions are allowed:
  - Use of immunosuppressive medication for the management of IP-related AEs (as per Appendix 8) or colitis events (as per Appendix 5)
  - Use of topical, inhaled or intranasal corticosteroids.
  - Systemic steroids at doses less than 10 mg/day prednisone equivalent.

### **2.3.1.2 Allowed medication**

Patients will be permitted to receive appropriate supportive care measures as deemed necessary by the treating physician including but not limited to the items outlined below:

- Opiates may be used for pain control and patients can receive preventive treatment for constipation
- Hormone therapies are allowed for patients who have been identified as a hormone therapy user at the start of the study
- Anticoagulant Therapy: patients who are taking warfarin may participate in this trial; however, it is recommended that prothrombin time (international normalised ratio (INR) and activated partial thromboplastin time (APTT)) be monitored carefully at least once per week for the first month, then monthly if the INR is stable. Subcutaneous heparin is permitted.
- Diarrhoea: Diarrhoea should be promptly treated in line with the colitis management and treatment guidelines Appendix 5. Anti-diarrheal agents should not be taken prophylactically.
- Corticosteroids: Patients may receive on-study treatment oral or intravenous (i.v.) glucocorticoids for up to 4 weeks (at daily doses equivalent to  $\leq 10$  mg of oral (p.o.) prednisolone). If steroids are required for treatment of colitis (as per Appendix 5), then study treatment should be held until steroids are tapered to  $\leq 10$ mg per day prednisone or equivalent. . Patients enrolled on Module 2 (RXC004 and nivolumab) may also receive treatment with steroids for immune-mediated AEs (as per Appendix 8. Steroids should be tapered to  $\leq 10$  mg/day prednisone or equivalent before re-starting nivolumab. Patients who require treatment with  $\geq 10$ mg per day prednisone or equivalent for  $>8$  weeks should permanently discontinue study treatment (RXC004 and nivolumab if applicable).
- Patients may receive immunosuppressant (e.g. infliximab for colitis or mycophenolate for hepatitis) rescue medication required for colitis (as per Appendix 5) or nivolumab related immune mediated adverse events (as per Appendix 8). Steroid refractory patients that require immunosuppressant treatment should permanently discontinue study treatment (RXC004 and nivolumab if applicable).
- Nausea/vomiting: Anti-emetic treatment can be administered if required according to the guidelines of the participating centres, except for the first dose each patient takes. Nausea and vomiting should be treated aggressively, and strong consideration should be given to the administration of prophylactic anti-emetic therapy.
- According to standard institutional practice. Patients should be strongly encouraged to maintain liberal oral fluid intake.
- Anaemia: Transfusions may be used as clinically indicated for the treatment of anaemia, but should be clearly noted as concurrent medications.
- Neutropenia: Colony-stimulating factors including G-CSF, pegylated G-CSF or GM-CSF according to Institutional Standards are allowed after the first cycle of therapy, following discussion with the PI and the Sponsor physician.

- Patients already receiving erythropoietin at the time of screening for the study may continue it providing they have been receiving it for more than one month at the time study treatment is started. Prophylactic erythropoietin should not be started during the DLT period but may be started during Cycle 2 and after, following discussion with the PI and Sponsor physician.

### **2.3.1.3 Subsequent Therapies for Cancer**

Details of first and subsequent therapies for cancer and/or details of surgery for the treatment of the cancer, after discontinuation of treatment, will be collected. Reasons for starting subsequent anti-cancer therapies including access to other PORCN/Wnt pathway inhibitors or investigational drugs will be collected and included in the exploratory assessments.

### **2.3.1.4 COVID-19 Vaccinations**

COVID-19 vaccination is permitted before or during study treatment, with the exception of live-attenuated vaccines and replication-competent vector vaccines, which are prohibited within 4 weeks of starting study treatment and whilst on study treatment.

As COVID-19 vaccines are often prioritised for cancer patients, vaccination prior to the first dose of study treatment is advisable. Where possible, COVID-19 vaccinations should be given at least 72 hours before starting study treatment and study treatment should not commence until any acute AEs from vaccination have resolved to at least Grade 1. If this is not possible, Investigators should follow their local prescribing information and policies when considering whether a patient on study treatment should receive a COVID-19 vaccination. If COVID-19 vaccination is given during the study (including the screening period), then all relevant information should be recorded in the concomitant medication CRF (i.e. vaccine name, manufacturer, date(s) given and dose).

